(WOCBP) will be screened using urine pregnancy kits to test for beta HCG levels. These kits will be provided by the sponsor. The results of these kits will be used as the final determination of pregnancy for WOCBP. WOCBP who screen positive for beta HCG (i.e. are pregnant) will be excluded from the study for the safety of both the mother and her unborn child. Phlebotomy for plasma collection, eventual CBC with differential, and platelet count will be performed for each research visit. Urine and stool will also be collected for each study visit. In addition to phlebotomy, urine collection, and stool collection, research participants will also receive a physical exam for each research visit.

Waist and hip circumference will be measured during the screening visit only. For the second visit (i.e. enrollment), the research participant will also receive a physical exam along with a flexible sigmoidoscopy. The flex sigmoidoscopy will be performed under moderate sedation using propofol per usual anesthesia services. The flexible sigmoidoscopy will be used to gain access to the pouch and to take a mucosal tissue pouch biopsy.

Table 2. Research Participant Study Activities

Visit Procedures	Screening²	Enrollment	2 Week³ (+/- 3 days)	4 weeks (+/- 7 days)	3months (+/- 14 days)
Informed Consent Process	X				
Physical Exam	X	X	X	X	X
Urine pregnancy testing for WOCBP	X				
Phlebotomy	X	X	X	X	X
Labs and Specimen Processing:					
Stool collection	X	X	X	X	X
Plasma collection	X	X	X	X	X
Urine collection	X	X	X	X	X
CBC w/diff., platelet count ⁴	X	X	X	X	X
Flexible Sigmoidoscopy with Moderate Sedation		X			
Mucosal Biopsy Collection		X			
Waist and hip circumference measures	X				
Fecal Microbiota Transplant		X			

Modified PDAI	X (clinical)	X	X (clinical)	X(clinical)	X (clinical)
Quality of Life Questionnaires	X			X	X
Food Recall Questionnaire		X		X	X

²If both screening and enrollment visits occur within 7 days, research samples may not be recollected at the enrollment visit, at the discretion of the investigator

³The 2-week visit may be conducted over the telephone for subjects who live a significant distance from the study site and at the discretion of the study investigator. Biological samples will not be collected on subjects who complete visit via telephone, however subject may be asked to mail in a stool sample for testing

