4. BIOLOGICAL SPECIMENS TO BE ACQUIRED

1. *Fecal sample*- The patient will submit a stool specimen in a container for genomic analysis at week 0, week 2, week 4, and week 12. Prior to enrollment, the patients will undergo PCR testing for *C. difficile*, routine stool culture, and ova and parasites. Any remaining stool sample will be used for research purposes for microbiota evaluation by 16S sequencing.
2. *Mucosal Pouch Tissue* -A total of up to 6 mucosal biopsies will be taken during routine standard of care flexible sigmoidoscopy procedure in patients undergoing investigation for presumed pouchitis or for routine surveillance of the pouch in patients without pouchitis. Two to four will be sent to pathology for assessment of histology. Two to four biopsies will be obtained for research purposes. No more than a total of 6 will be taken. All non-research biopsies will be placed in saline and transported to the Pathology Department at Emory immediately. Research related

biopsies will be collected by the study team and transported to the Pathology Department at Emory University.

3. *Stool*- Additional stool will be collected after treatment 4 weeks and 3 months after fecal microbial transplant (FMT). If the first and second study visit occur within 48hours, the second collection of biologic samples will be at the discretion of the study doctor.

Samples collected through this study will be given a de-identified code that is not derived from or related to information about the individual and is not otherwise capable of being translated to identify an individual. The samples will then be barcoded and transported to a central core laboratory at Emory University managed by [name]. Fecal and mucosal samples will be saved and stored in locked refrigerators/freezers in [name] laboratory in the Woodruff Memorial Building. DNA will be extracted for sequencing at this laboratory using automated extraction. Sequencing of the 16S regions will be performed in [name] laboratory.

Plasma and urine samples will be collected from each patient at study visits as illustrated in the study procedures table, and will be barcoded and saved in locked freezers in [name] laboratory in the Woodruff Memorial Building until all the samples are collected. At such time, they will be transported to [name] laboratory in the Whitehead building for metabolomic profiling.

Biological samples will not be collected on subjects who complete study visits via telephone follow-up.

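### Two different limits, 7 days and 48 hours, for skipping the enrollment research samples; under the 7-day limit the only pre-FMT stool, plasma and urine can predate the latest permitted antibiotic/probiotic stop by up to 120 hours

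*Combined protocol and SAP*

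**What the plan says.** The default is to sample at every visit. The visit text in Section 3.6 states "Urine and stool will also be collected for each study visit", and Table 2 marks stool, plasma and urine at both screening and enrollment. Section 4, item 1, adds: "The patient will submit a stool specimen in a container for genomic analysis at week 0, week 2, week 4, and week 12".

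Two provisions relax this for the same pair of visits:

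- Table 2, footnote 2: if "both screening and enrollment visits occur within 7 days, research samples may not be recollected at the enrollment visit". The decision is left to the investigator.
- Section 4, item 3: "If the first and second study visit occur within 48hours, the second collection of biologic samples" is left to the study doctor.

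The text around Table 2 identifies the second visit as enrollment, which is also the transplant visit. Section 3.6 b requires subjects to be off antibiotics and probiotics for a minimum of 48 hours before the transplant. It does not link the screening samples to that stop.

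Section 3.7 has fecal microbiome and metabolomic profiles analyzed before therapy and four weeks after it. Section 4 covers the other fluids: "Plasma and urine samples will be collected from each patient at study visits", for metabolomic profiling.

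**The concern.** For a gap of, say, five days, footnote 2 permits the enrollment samples to be skipped, while Section 4 offers no such discretion and the default is to collect. Staff following different pages would create different baselines.

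This matters because of who is enrolled. Section 1 names chronic antibiotic-dependent pouchitis as a target condition, so some subjects may well be on antibiotics at screening. If the screening sample then stands in for the enrollment sample, it may have been taken under antibiotics, while another subject's baseline was taken after the stop. Aim 2 is the change in the microbial environment from before to after treatment. In a single-arm study no comparator separates the effect of stopping antibiotics from the effect of FMT, so uneven baselines add an avoidable component to that change.

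Sections 3.7 and 5 record antibiotic history and prescribed medicines, but the available text does not attach a last-dose date to each sample. The affected baselines might therefore not be identifiable afterwards.

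**Working it through.** The plan gives no figure for this point, so there is none to reproduce. The check is elapsed-time arithmetic with FMT at the enrollment visit as time 0.

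**Inputs**
- Waiver window, Table 2 footnote 2: 7 days = 7 × 24 = 168 h.
- Waiver window, Section 4 item 3: 48 h.
- Latest permitted antibiotic/probiotic stop, Section 3.6 b: 48 h before FMT.
- Earliest preparation enema, Section 3.6 b: 3 h before the procedure.

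**Step 1. Where the waivers disagree.** They differ for visit gaps above 48 h and up to 168 h, a band of 168 − 48 = 120 h.

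**Step 2. How far the sole baseline can precede the stop.** If the enrollment samples are skipped, the screening sample is the only pre-FMT sample. Its maximum lead over the latest permitted stop is max(0, gap − 48 h).

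| Gap between visits | Maximum lead over the stop | Skipping allowed by |
|---|---|---|
| 1–2 days | 0 h | both rules |
| 3 days | 72 − 48 = 24 h | footnote 2 only |
| 4 days | 96 − 48 = 48 h | footnote 2 only |
| 5 days | 120 − 48 = 72 h | footnote 2 only |
| 6 days | 144 − 48 = 96 h | footnote 2 only |
| 7 days | 168 − 48 = 120 h | footnote 2 only |

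Under Section 4 the maximum is 48 − 48 = 0 h: a waived subject's screening sample is no earlier than the latest permitted stop.

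**Step 3. Which samples are exposed.** Stool, plasma and urine are scheduled at both visits and can be waived at the second. Mucosal biopsies are scheduled only at enrollment, so there is no screening biopsy to stand in for them. The primary endpoint in Section 10 uses the clinical component of the modified index, not these samples.

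**Step 4. Is a clean enrollment stool obtainable?** Between the latest permitted stop and the earliest enema there are 48 − 3 = 45 h, and more if the subject stops earlier. A stool passed after the stop and before the enemas is therefore possible in time.

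**The case against.** The strongest reply is that this is one mismatched number between two waivers in an 11-patient pilot without a power calculation, and that it does little harm. Several parts of that stand.

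- The 120 h needs four things together: a subject on antibiotics or probiotics at screening, a 7-day gap, a stop at the last permitted moment, and a decision to skip. It is a bound on timing, not an estimate of bias.
- The documents give neither the number of such subjects nor the size of any shift. The paired tests named in Section 9 are for PDAI and quality-of-life scores. No false-positive rate can be derived.
- Most of the confounding of antibiotic withdrawal with FMT comes from the single-arm design and is present under either waiver. A baseline taken just after the stop still precedes any later recovery, and the documents do not show how far it differs from an on-antibiotic sample.
- A reader might infer that the visit text and the week-0 stool are absolute requirements that footnote 2 violates. They are not: Table 2's footnotes qualify the visit text, and item 3 qualifies item 1 within Section 4. The conflict is between the two waivers.

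The reply does not remove the inconsistency. Both waivers govern the same decision, they give different answers over a 120 h band, and only one keeps a sole baseline from preceding the required stop.

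**Conclusion.** The two waivers conflict. Under the 7-day waiver, the only pre-FMT stool, plasma and urine of a subject on antibiotics or probiotics at screening can precede the latest permitted stop by up to 120 h; under the 48-hour waiver the maximum is 0 h. On- and off-antibiotic baselines can then be mixed in the before/after microbiome and metabolome comparison. This should be corrected, but it bears on Aim 2 and not on the clinical primary endpoint.

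The figures assume that windows are counted in exact hours from FMT at the enrollment visit (counting calendar days could move them by some hours) and that footnote 2 is permissive, since it leaves the choice to the investigator.

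Two stronger readings are not supported. One is that the microbiome comparison is invalid as planned: exposure is limited to subjects on these agents whose enrollment samples are skipped, and their number is unknown. The other is that the donor reference in Section 10 cannot be established. The available text describes no profiling of donor material, but some text was removed before review. The storage sentence, "Fecal and mucosal samples will be saved and stored in locked refrigerators/freezers", is also not expressly limited to patients, although the numbered items around it concern patient specimens. That is a separate, secondary point.

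**What to change.** Reconcile the two passages through the sampling rule only, leaving every treatment rule as it stands:

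1. Put the Section 4 window of 48 hours into Table 2 footnote 2. A screening sample used as the sole baseline then falls no earlier than the stop that Section 3.6 b already requires.
2. For longer gaps, collect the scheduled enrollment stool, plasma and urine and label them as the week-0 baseline. Where feasible, take the stool before the preparation enemas. This is a precaution, since the documents do not measure the effect of the enemas on the sample.
3. Record the date of the last antibiotic and the last probiotic dose with each sample, before and after FMT.
4. If any baseline was nevertheless taken before the stop, repeat the before/after analysis without it. If the rule is followed, this will concern deviations only.
5. State in the report that recovery continuing after a short antibiotic-free interval remains mixed with the FMT effect.

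The cost is one date field per sample and, for each of the 11 subjects at most, one repeat set that Table 2 already schedules. Stool before the enemas may need home collection, with instructions for storage and transport. The existing provision that a "subject may be asked to mail in a stool sample for testing" belongs to the 2-week telephone visit and would not cover this.

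Separately, it is advisable to keep an aliquot of each donor preparation and to state how the donor reference is profiled. How similarity to the donor is then measured is for the sponsor to choose.

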All activities outlined in **Table 1** would be billed to the sponsor to compensate [name] for her time and effort to support our participants and overall project goals and needs. The donor related activities will take place before the research participant is seen for informed consent during the screening visit (see **Table 2**). This is done to ensure that the donor has been screened for infectious diseases in a timely manner and that [name] has ample time to prepare the allogenic human fecal specimen in her lab for the transplant on the enrollment visit. Donors will be screened every four weeks which is standard protocol for [name] lab. More details about the donor screening process and requirements are listed in the protocol section **3.6 a) Donor Stool Collection and Processing**.

Table 1. Donor Related Study Activities

Donor Activity	Specific Test Ordered	Visit
Blood/Serology Testing	
 1. Hepatitis A IgM and IgG 2. Hepatitis B S Ab/Sag/Core Ab 3. Hepatitis C Ab 4. RPR 5. Human Immunodeficiency Virus (HIV) 1 and 2 Antibody 	Donor Screening (every four weeks)
Stool Testing	
 1. Clostridium Difficile PCR 2. Salmonella, Shigella, and Campylobacter 3. Ova and parasites 4. H. Pylori antigen 5. 5.Vancomycin resistant Enterococcus (VRE) 6. Carbapenemase resistant Enterobacteriaceae 	
Fecal Sample Preparation for Donation ¹	N/A	

¹The fecal sample will be prepared for the FMT in [name] laboratory on site. Please refer to section 3.6 a for more detailed information regarding the donor fecal sample processing activities.

Table 2 outlines a total of five complete research visits for each research participant: screening (initial), enrollment (transplant), 2 weeks post-transplant (may be a phone call at the discretion of the physician), 4 weeks post-transplant, and 3 months post-transplant. For the initial or screening visit, research participants will first complete the informed consent process with a member of the research team. Upon completion of the informed consent process, the participant will receive phlebotomy to collect blood for plasma chemistries, CBC with differential, and platelet counts.

Urine will also be collected and screened for basic urinalysis. Women of child bearing potential

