Timeline: All the proposed aims and enrollments will be carried out within 24-month period. We do anticipate a large proportion of eligible subjects may travel to Emory as the interest in this therapeutic platform is quite high with us already receiving numerous requests.

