10. ENDPOINTS

The primary endpoint of this study will be resolution of clinical pouchitis symptoms using the clinical component of the modified pouchitis disease activity index without relapse for 3 months. Secondary endpoints include 16S ribosomal gene sequencing and metabolomic profiles that are more favorable (as defined by the donor microbiota). An additional secondary endpoint will be improvement of quality of life as determined by QOL questionnaires.

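### A telephone visit is provided for only at week 2, so a relapse-free subject who cannot return at month 3 has no primary outcome, although a call could supply it

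*Combined protocol and SAP*

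**What the plan says.** **Telephone option.** The Section 3.6 text introducing Table 2 lists the follow-up visits as "2 weeks post-transplant (may be a phone call at the discretion of the physician), 4 weeks post-transplant, and 3 months post-transplant". The call is attached to the first of the three only. Footnote 3 to Table 2 repeats this: the "2-week visit may be conducted over the telephone for subjects who live a significant distance from the study site", again at the investigator's discretion. Section 4 ends more loosely: "Biological samples will not be collected on subjects who complete study visits via telephone follow-up". The plural is not tied to week 2, but the sentence only withholds samples. It does not create a telephone visit at any other time.

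**Primary endpoint.** Section 10 defines it as "resolution of clinical pouchitis symptoms using the clinical component of the modified pouchitis disease activity index without relapse for 3 months".

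**What month 3 requires.** The row "Modified PDAI" in Table 2 is marked as clinical only at screening, week 2, week 4 and month 3. The row "Flexible Sigmoidoscopy with Moderate Sedation" is marked at enrollment only, as is biopsy. Month 3 also carries a physical exam, blood, plasma, urine, stool and the questionnaires. The windows are 7 days either side at week 4 and 14 days either side at month 3.

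**Distance and size.** The timeline paragraph closing Section 3.6 states: "We do anticipate a large proportion of eligible subjects may travel". It gives no number. Section 6 sets enrolment at 11. Section 9 gives no power calculation, dropout allowance, analysis set or rule for missing outcomes.

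**The concern.** The plan recognises that distance may keep a subject from a visit, and relieves it at the first follow-up visit but not at the visit that completes the primary endpoint. The score needed at month 3 involves no procedure, so losing it for want of travel is avoidable.

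The loss may also be related to outcome. A subject who relapses may be treated near home and not come back, and one who feels well may see no reason to travel. These push the observed rate in opposite directions, and the data would not show which had happened. The result is meant to inform, through a Simon two-stage rule, whether more patients are enrolled. With 11 subjects, one or two unknown outcomes leave a visible gap in the response rate.

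**Working it through.** **Step 1. Can the score be obtained without a visit?** The clinical items in Appendix 1 are:
- stool frequency against the subject's postoperative usual: reported by the subject;
- rectal bleeding: reported by the subject;
- urgency or cramps: reported by the subject;
- fever at 37.8 °C or above: needs a thermometer reading, which can be taken at home.

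None needs endoscopy, histology or a laboratory test.

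**Step 2. Who would have no outcome?** The endpoint requires freedom from relapse up to 3 months. A relapse recorded at week 2 or week 4 already decides the outcome as failure. A subject with no relapse recorded by then can be classified only with month-3 information. The gap therefore concerns this second group.

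**Step 3. Size.** The plan offers no figure to reproduce: the sample size of 11 has no stated derivation, and the Simon design is named without response rates, error rates or stage sizes. The following is illustration.

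Inputs: N = 11 (Section 6); x = 3 responders seen and m subjects missing (both assumed). Outcomes of the m subjects are taken as not already settled by an earlier relapse.

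- Weight of one subject: 1/11 = 9.1 percentage points.
- Observed rate: x/(11 − m).
- Lowest possible rate in all 11: x/11.
- Highest possible rate in all 11: (x + m)/11.
- Intervals: exact (Clopper-Pearson) 95%.

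| m | Observed rate | Exact 95% CI | Possible rate in all 11 |
|---|---|---|---|
| 0 | 3/11 = 27.3% | 6.0% to 61.0% | 27.3% |
| 1 | 3/10 = 30.0% | 6.7% to 65.2% | 27.3% to 36.4% |
| 2 | 3/9 = 33.3% | 7.5% to 70.1% | 27.3% to 45.5% |
| 3 | 3/8 = 37.5% | 8.5% to 75.5% | 27.3% to 54.5% |

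With two missing, the unresolved range is 2 × 9.1 = 18.2 percentage points.

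**Step 4. How likely is a complete set?** If subjects are lost independently at an assumed rate r, the chance of all 11 outcomes is (1 − r)^11 and the expected loss is 11r:
- r = 5%: 0.95^11 = 57%; expected loss 0.55;
- r = 10%: 0.90^11 = 31%; expected loss 1.1;
- r = 15%: 0.85^11 = 17%; expected loss 1.65;
- r = 25%: 0.75^11 = 4%; expected loss 2.75.

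**The case against.** **The later visits are in person for a reason.** The primary objective is safety and tolerability. Week 4 and month 3 carry an exam, blood counts and samples, and week 4 is the named post-treatment time for the microbiome and metabolomic analysis. A written telephone option might displace visits that would have taken place. This stands, and it is why the option should be a fallback only.

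**Calls are not forbidden.** A reader might infer that the protocol bars a telephone score at month 3. It does not: such a call is unprovided for, and the plural in Section 4 leaves the intention unclear. But no text says that a score taken that way would count, and deciding so after seeing who stayed away invites bias.

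**Distance is not loss.** A reader might take the timeline paragraph as a forecast that many subjects will fail to return. It is a recruitment remark that cites strong interest, gives no share of distant subjects and no loss rate. The visit windows also already give travellers some room.

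**Not every absent subject lacks an outcome.** An earlier recorded relapse settles the matter without month 3. Section 10 does not say by which visit resolution must be reached, so the text does not show whether symptoms persisting at week 4 also settle it.

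**The week-2 column proves little.** Table 2 marks the clinical score at week 2, where a call is allowed, but it marks a physical exam there too, which a call cannot provide. The mark alone does not show that the score is taken by telephone. The argument rests on the content of the items.

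**Missing outcomes would not dominate.** A reader might infer that one or two missing outcomes swamp the result. In the illustration, the range of 27% to 45% lies well inside the complete-data interval of 6% to 61%, so sampling error is the larger uncertainty. The difference is that sampling error is unavoidable at this size, while this loss is not.

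**Conclusion.** The point holds as a gap in the follow-up provisions, not as a contradiction or a demonstrated loss. A relapse-free subject who does not return at month 3 has no primary outcome under the plan as written, although a call could supply one, and no rule says how that subject is counted.

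The weight of 9.1 percentage points per subject follows from the planned 11. The other figures rest on assumed counts and loss rates. Because the Simon rule has no parameters, it cannot be said whether one or two missing outcomes would change the decision on further enrolment. The change is worth making because it is cheap and protects the primary endpoint; it does not remedy the imprecision of a pilot of 11.

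**What to change.** - **Table 2, footnote 3, and the visit list in Section 3.6:** allow a telephone contact at week 4 and month 3 only when the subject cannot attend, within the existing windows. In-person attendance remains the default.
- **Content of the call:** clinical mPDAI with a home temperature reading, adverse events and antibiotic use. Send the QOL forms by mail. Record the mode of collection for each score.
- **Section 4:** reconcile its closing sentence with the footnote. State which visits may be by telephone, and whether the mailed stool sample that the footnote mentions, and Section 4 does not, applies.
- **Section 9:** analyse all treated subjects. Keep a relapse already recorded as non-response. Count a subject as a non-responder for missing data only when no contact is made in the window.

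**Cost.** An amended footnote, matching edits in Sections 3.6 and 4, a short addition to Section 9, and a call by existing staff. A telephone contact yields no exam, blood or urine, and fever is self-measured. If the fallback were used freely, it would displace safety laboratory tests and research samples, hence the restriction to subjects who cannot attend.

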⁴ Screening labs for hemoglobin (Hgb), platelet count, and absolute neutrophil count (ANC) may be performed within six months of screening visit

3.6. a) Donor Stool Collection and Processing

The standard donor stool will be obtained from a donor who has undergone testing for potential transmittable infections. These include Hepatitis A, Hepatitis B, Hepatitis C, syphilis, HIV, *H pylori*, *Salmonella*, *Shigella*, *Campylobacter*, *C. difficile*, as well as screening for ova and parasites, and multidrug resistant organisms (specifically carbapenemase-producing *Enterobacteriaceae* and vancomycin-resistant *Enterococcus*). This testing is performed through Emory Medical Laboratories. In addition, the donor will be screened for illnesses that would exclude him from donating stool for the current study (see attached screening questionnaire). Donor screening will be completed and all results confirmed negative prior to use of donor stool for transplant. Standard donors will be re-screened every six months.

The standard donor voids the stool at home just prior to leaving for work in the morning. The stool is dropped off in the microbiology laboratory within 60 minutes of being voided. The stool is processed within 60 minutes of the drop off, and administered within 120 minutes of the processing. The time that elapses from the stool being voided by the donor and administered to the patient ranges from 60-240 minutes. Donor stool will be handled as a level 2 biohazard with appropriate universal precautions.

Appropriate Personal Protective Equipment (PPE) will be worn by personnel while handling/processing donor fecal material:

- Nitrile gloves will be worn while working with all potentially infectious agents. Gloves should be removed before touching common objects in public areas. Hand washing will be performed each time gloves are changed.
- Gloves should be removed prior to removal of other PPE. Gloves should be removed before leaving the laboratory.
- Lab coats will be worn over clothing while handling/processing stool specimen and preparing FMT solution

FMT in UC-associated Pouchitis

Version 3.0, date finalized 06/26/2017

- Contaminated clothing will be decontaminated and laundered on-site or by a commercial laundry service.
- Protective eyewear/goggles will be used, if splash potential exists
- Laboratory access will be limited to authorized personnel only.

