3.7 Inclusion and Exclusion criteria

The following lists outline key criteria used by the principal investigator, sub-investigators, and study team to determine who can and cannot be in this study.

Inclusion Criteria

1. Males and females between the ages of 18 and 80 (inclusive) with ulcerative colitis-associated IPAA with and without pouchitis
2. Eligible patients will be identified through the Emory Clinic (TEC), St. Joseph's Hospital (SJH), and Emory University Hospital (EUH)
3. Signed informed consent

Exclusion Criteria

1. Age <18 years or >80 years of age
2. Exposure to immunosuppressive therapy within the 4 weeks prior to enrollment or their expected use within 1 month of FMT
3. Concomitant *Clostridium difficile* infection
4. Suspected Crohn's disease
5. Documented active infection of any kind
6. Patients on anti-coagulant therapy, with platelet count less than 50,000, significant anemia with hemoglobin < 7, or those with other conditions that place them at increased risk of bleeding
7. Pregnant or breastfeeding women (pregnancy will be verified using urine pregnancy kits)
8. Need for imminent surgery
9. Absolute neutrophil count (ANC) < 1000 or history of opportunistic infection
10. Administration of any investigational drug within one month before FMT

Demographic data, including prior history of pouchitis with sub-classification into chronic antibiotic resistant (refractory) pouchitis, chronic antibiotic use as well as previous treatments will be recorded. Measures of waist and hip circumference and waist to hip ratio will be calculated and recorded. Stool samples, urine, and serum samples will be collected. Patients will be screened at entry for enteric pathogens (*C. difficile*, routine bacterial stool culture, ova and parasites) and positive results will exclude entry to the study.

Fecal samples from subjects will be analyzed for microbiome genetics, and metabolomic profiles before and four weeks after therapy. Scored symptoms according to the modified pouch disease activity index (mPDAI) (**Appendix 1**) as proposed by Shen et al. will also be recorded.

FMT in UC-associated Pouchitis
Version 3.0, date finalized 06/26/2017

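### Table 2 footnote 4 lets the hemoglobin, platelet and neutrophil exclusions rest on a count up to six months old at screening, and no section requires a current count to be read before biopsy and FMT

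*Combined protocol and SAP*

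**What the plan says.** Section 3.7 sets the laboratory limits. Exclusion 6 covers "Patients on anti-coagulant therapy, with platelet count less than 50,000, significant anemia with hemoglobin < 7", together with any other raised bleeding risk. Exclusion 9 is "Absolute neutrophil count (ANC) < 1000 or history of opportunistic infection". Neither says how recent the count must be.

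The timing comes from Section 3.6. After consent at the screening visit, "the participant will receive phlebotomy to collect blood for plasma chemistries, CBC with differential, and platelet counts". More generally, "Phlebotomy for plasma collection, eventual CBC with differential, and platelet count will be performed for each research visit". Table 2 marks the CBC row at all five visits, including enrollment, which is also the visit for sigmoidoscopy, biopsy and FMT. Footnote 4 is attached to that row and relaxes the screening entry: "Screening labs for hemoglobin (Hgb), platelet count, and absolute neutrophil count (ANC) may be performed within six months of screening visit".

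**The concern.** A laboratory exclusion protects a patient only if the value describes the patient at the time of exposure. Exclusion 6 plainly bears on bleeding from up to six pouch biopsies, and exclusion 9 on infection after donor stool. Safety and tolerability are the primary objective (Section 3.1).

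Counts can move over six months. Exclusion 2 bars "Exposure to immunosuppressive therapy within the 4 weeks prior to enrollment", so it looks back only four weeks. A historical count could predate a course of immunosuppression that began afterwards and ended before that window opened. Daily rectal bleeding is also a scored symptom in Appendix 1, so hemoglobin could drift in this population. Both are illustrations. The documents do not say how often patients cross these thresholds.

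The question is therefore whether a patient who is below a threshold on the day of the procedure could be biopsied and transplanted with every written rule followed.

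**Working it through.** No formula decides this point. It rests on setting the sections side by side, with one short calculation of age.

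**1. Which values decide eligibility.** Exclusions 6 and 9 use hemoglobin, platelets and ANC. Footnote 4 names the same three.

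**2. Which date applies.** The exclusions give none, and footnote 4 gives six months around the screening visit. The wording does not say before or after; before is the natural reading.

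**3. Whether a newer count must take over.** Newer counts are scheduled, so the test is whether any section makes one decisive before the procedure.

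| Place | Content | Review of the recipient's count required first? |
|---|---|---|
| Section 3.6 text and Table 2 | CBC drawn at screening and at every visit | No |
| Section 3.6 b) | Pouch preparation, loperamide, positioning, monitoring after FMT | No |
| Section 3.7, biopsy text | Biopsies first, then FMT | No |
| Section 4 | Stool, tissue, plasma and urine collection | No |
| Section 7 | Biopsy and FMT risks, technique to reduce them | No |

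**4. Whether the plan writes such a rule for anything else.** It does so for the donor: "Donor screening will be completed and all results confirmed negative prior to use of donor stool for transplant". That is the only explicit confirm-before-use rule. The recipient stool-pathogen sentence in Section 3.7 says that a positive test excludes. That is an eligibility rule of the same kind as exclusions 6 and 9, so it does not serve as a contrast.

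**5. Age of the deciding count.** Age at procedure = six months + screening-to-enrollment interval.

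- Six months = 6 × 365.25 / 12 = 182.6 days.
- The interval has no stated maximum. Section 9 says only that the procedure takes place at a follow-up visit. Footnote 2 (7 days) and Section 4 (48 hours) describe what happens if the visits are close together; they do not require it.
- For assumed intervals of 0, 7, 14 and 28 days: 182.6 + 0 = 182.6; 182.6 + 7 = 189.6; 182.6 + 14 = 196.6; 182.6 + 28 = 210.6 days.
- If a visit CBC decides instead, the age is 0 days for the enrollment CBC. For the screening CBC it equals the interval, 0 to 28 days under the same assumption.

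**6. What the bleeding rate in Section 7 can and cannot show.** Section 7 gives significant biopsy bleeding as 1 in 1,000. Read per patient, the chance of at least one event is 1 − 0.999^11 = 1.1%. Read per biopsy, with 11 × 6 = 66 biopsies, it is 1 − 0.999^66 = 6.4%. These are background figures for the whole study. They apply whichever count is used, and the documents give no rate for patients below the thresholds, so neither figure measures this gap.

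**The case against.** The strongest case against is that the controls already exist. A CBC is drawn after consent and another at enrollment. Footnote 4 is permissive and touches only the screening result. Exclusions 6 and 9 are not confined to the screening value, so an investigator who saw a low enrollment count would have grounds to stop. Anticoagulants, other bleeding risks, active infection, past opportunistic infection and recent or expected immunosuppression are excluded separately. The allowance also has a plausible purpose: the timeline in Section 3.6 expects that many eligible patients may travel, and accepting an existing count would suit them. No standard in the documents makes six months an error in itself.

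Most of this stands, and it is why the stake is small. It does not remove the gap. Drawing blood is not the same as reading the result, and footnote 4 lets the older value satisfy the eligibility review.

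A reader might infer that patients could be treated with no recent blood count at all, particularly through footnote 2, which allows research samples not to be taken again at enrollment when the visits fall within 7 days. The documents do not support that. The CBC stays scheduled at both visits, footnote 2 speaks of taking samples a second time and so presupposes a first, and it does not say that the CBC is a research sample. Nor should the word eventual in Section 3.6 be read as a statement that results arrive after the procedure.

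**Conclusion.** The point holds as a minor but real eligibility gap. Exclusions 6 and 9 may be judged on a count about 183 days old at screening, or about 183 to 211 days old at the procedure if the interval is 0 to 28 days. The interval is an assumption. No section makes review of a current count a condition for biopsy and FMT.

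It is more than missing detail, because a written permission allows the weaker practice. A patient now below a threshold could be treated without any protocol deviation.

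The size of any harm cannot be estimated from the documents. At most 11 patients are concerned, the number who would rely on footnote 4 is unknown and may be zero, and the thresholds are low. A reader might take the 1.1% or 6.4% as the risk created by footnote 4. The documents do not support that, because both are background bleeding risks that would remain after the change. No endpoint, sample size or planned analysis is affected. The conclusion rests on the protocol text available for review and on reading six months as the period before screening.

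**What to change.** Amend footnote 4 along these lines: *A result from the six months before the screening visit may be used for pre-screening only; a CBC drawn at the screening or enrollment visit must be resulted and reviewed against exclusions 6 and 9 before biopsy and FMT.* No separate change to footnote 2 is needed, since this sentence already guarantees one reviewed visit CBC.

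The cost is one sentence. The CBCs are already in Table 2 and covered under Section 14.2. Historical counts remain useful for deciding whom to invite, including patients who travel. The only burden falls on patients who would otherwise have relied on a historical count: a draw at screening, or a short wait for the result at enrollment. The screening draw is the easier route because the stool is time-limited: "The time that elapses from the stool being voided by the donor and administered to the patient ranges from 60-240 minutes". With the count reviewed before the enrollment visit, nobody has to weigh a pending result against that window.
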